1.1 Non-Clinical and Clinical Study Findings

Potential Benefits: Research is designed to benefit society by gaining new knowledge. This study is not designed to benefit participants. Affective disorders are prevalent and representative an enormous public health burden. This study offers the general benefit of advancing our understanding of the brain circuitry that may be altered by the menstrual cycle in women with PMDD. In other ongoing studies, our results show enhanced alpha oscillations by tACS in patients with schizophrenia or depression, with associated decreased hallucinations in the former and depressive symptoms in the latter.

Risk/Benefit Assessment: Transcranial current stimulation has been used in hundreds of studies without any reports of serious side-effects (Brunoni and Amadera 2011). In our experience to date in studies of patients with schizophrenia and with depression, no serious adverse events have been reported. Therefore, transcranial current stimulation represents an extremely safe and non-invasive therapeutic approach.

Passing weak electric current through the scalp is also routinely done for measuring electrode resistance in all EEG recordings, a known safe procedure. Importantly, this stimulation mode has nothing to do with electroconvulsive therapy, which applies many orders of magnitude higher stimulation current. Rather, transcranial current stimulation is so weak that it does not produce super-threshold activation of neurons ([name] and McCormick 2010). There is a rare/theoretical likelihood that stimulation of neuronal circuits can lead to seizure. However, no studies have reported seizure as a side effect in recent trials of tDCS for depression or schizophrenia (Brunelin et al., 2012; Berlim et al. 2013) (nor in any trials to date). To further minimize this very small, theoretical likelihood of a seizure, we screen and exclude patients with personal and family history of neurological conditions from the study.

When comparing input of energy into the subject, both the amount of current and the area over which this current is dispersed are critically important. The value of interest is called the current density, which is the amount of current divided by the area. Our stimulation area is 25 cm². Therefore, we will use this device at 2mA, resulting in a current density of 0.08mA/cm². Our use of this transcranial current stimulation device poses 'minimal risk' to subjects because of the low current density being applied. Our application of current will result in an equivalent current density as performed in prior studies, in which subjects experienced no serious side-effects or harm. Prior studies using other brain stimulators have used a range of current densities: (Iyer, Mattu et al. 2005) used a maximum current density 0.08mA/cm², conducted at NINDS with DC stimulators, and (Groppa, Bergmann et al. 2010) used a maximum current density of 0.125mA/cm² with no reported side effects

With use of this technology, some subjects report transient tingling underneath the electrode on the scalp, itching, headache, burning sensation, and discomfort. However, a recent meta-review has

failed to find any significant difference in occurrence rates between transcranial current stimulation and sham control itching (39.3% vs. 32.9%, $p>0.05$), tingling (22.2% vs. 18.3%, $p>0.05$), headache (14.8% vs. 16.2%, $p>0.05$), burning sensation (8.7% vs. 10%, $p>0.05$) and discomfort (10.4% vs. 13.4%, $p>0.05$). (Brunoni, Amadera et al. 2011). In our experience, increased sleepiness and flickering lights were more common than sham stimulation. During stimulation, the research assistant will ask the subject about her comfort level. If the subject reports any pain, stimulation will immediately be stopped.

EEG: EEG is a commonly used measure and is not associated with adverse events. Individuals may find the electrode gel annoying, as hair will require shampooing after the conclusion of the EEG.

Embarrassment: Self-report assessments contain questions regarding sensitive personal information. This risk is necessary to assess mood symptoms and psychopathology. Subjects will be assured upon intake that only study personnel will see associated DRSP responses.

Confidentiality breach: A breach of confidentiality could indicate to others a participant's history of PMDD. Risk of breach of confidentiality is minimized by identifying research subjects by a study number on all research documents. Study documents that must contain personal information, including the informed consent document will be kept in filing cabinets in locked rooms. The document that links study ID number to personal identifying information will be kept electronically on a UNC password protected server. All data will be stored in locked cabinets inside locked offices. Electronic data will be stored only on password-protected computers, and data encryption methods will be used during communication between investigators. Only study personnel will have access to these data. All study staff participate in annual human subject training that includes education about responsibilities to the minimize risk of confidentiality breach.

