Subject Population	
Inclusion Criteria:
 
 Age 18-52

key criteria for Inclusion and Exclusion:	
 · Have a prospectively confirmed diagnosis of PMDD · Regularly menstruating without hormonal contraceptives · Medication free or regularly taking medication that has no effect on the nervous system · Not currently pregnant or planning to become pregnant 
Exclusion Criteria:
 
 · Brain surgery or brain implants, including cochlear implants or aneurysm clips · Neurologic disease (e.g. epilepsy or brain tumor) · Traumatic brain injury · Pregnant or nursing · An unstable medical illness (e.g. congestive heart failure or end-stage kidney disease) · History of severe or recurrent substance abuse within 2 years of study enrollment · History of suicidal behavior within 5 years of study enrollment · UNC Department of Psychiatry faculty, employee, or trainee
Number Of Subjects	20
Study Duration	
Each subject's participation is expected to last approximately one month. Two tACS with EEG recording sessions will occur, one during the follicular phase (5-9 days after menstruation) and one in the luteal, premenstrual phase (9-13 days after ovulation). Subjects will test their urine at home each morning for approximately one week to determine ovulation. Each tACS/EEG session will last up to 90 minutes.
 
The entire study is expected to last four and a half years

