3.4 Study Population

-Inclusion and Exclusion Criteria

Subjects will be women with PMDD. All subjects will have had their diagnoses confirmed by participation in our diagnostic study. The diagnosis requires demonstration of at least a 30% increase in symptom ratings in the seven days preceding menses compared with the seven days following the cessation of menses in two of three menstrual cycles.

In addition to PMDD diagnosis, all women enrolled must also meet the following criteria:

Inclusion Criteria:

- Age 18-52
- Have participated in our PMDD diagnostic study
- Regularly menstruating without hormonal contraceptives (e.g., birth control pills, injections, implants, progestin IUDs)
- Medication free or regularly taking medication that has no effect on the nervous system
- Not currently pregnant or planning to become pregnant
- With sufficient resource to prevent pregnancy

Exclusion Criteria:

- Brain surgery or brain implants (e.g., cochlear implants or aneurysm clips)
- Neurologic disease (e.g., epilepsy or a brain tumor)
- Traumatic brain injury
- Pregnant or nursing
- Any unstable medical illness (e.g., congestive heart failure or end-stage kidney disease)
- History of severe or recurrent substance use disorder, or any substance abuse within 2 years of study enrollment
- History of suicidal behavior within 5 years of study enrollment
- UNC Psychiatry faculty, employee, or trainee
-

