4.2 Intervention/Treatment procedures (by visits)

Effect of Menstrual Phase on Target Engagement

Transcranial Current Stimulation: Subjects will report for bilateral stimulation with tACS (one session) per menstrual phase, over the course of one menstrual cycle (unless it is an anovulatory cycle, in which case the participant will be asked to conduct the ovulation testing for one additional cycle). Each participant will receive tACS once in the follicular cycle phase and once in the luteal cycle phase, in counterbalanced order. The tACS stimulation will deliver a maximum amplitude of 2mA for a total of 40 minutes of stimulation per session. Electrodes will be saline soaked, 5x5cm, and placed over F3 and F4 locations to target dorsolateral prefrontal cortex. The return electrode will be located over CZ. A transcranial current stimulator designed by the [name] lab (XCSITE100 stimulator) will be used. After the first tACS session, participants will be instructed to begin daily mood ratings as recorded in the Daily Record of Severity of Problems via electronic Qualtrics survey. This 20-item self-report rating scale assesses physical and mood symptoms that accompany ovarian hormone changes and is often used as a dimensional measure of PMDD.

Electroencephalography (EEG): Each EEG session will last 8 minutes, and participants will alternate between having eyes open and closed at 2-minute intervals. A total of four EEG recordings will be performed throughout participation; two recordings per menstrual phase to be collected before and after stimulation. EEG will be recorded with a standard Nicolet v32 clinical EEG machine that is approved for clinical use and that has been used in all previous studies by the [name] Lab. Briefly, 10mm gold cup electrodes are fitted to the individual participants for brief, non-invasive recordings of brain activity.

4.3 Follow- up procedures (by visits): Will be scheduled only as necessary to assess acute suicidal ideation, severe mood deterioration, or severe somatic symptoms.

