7 STUDY INTERVENTION

Device Description: XCSITE100 Stimulator

We will be using the XCSITE100 stimulator designed in the [name] Lab for investigational purposes. The device is not implanted and has not been designed for or being used to support or sustain human life. This device does not have a potential for serious risk to the health, safety, or welfare of the participant. There has never been an instance of serious side-effect reported due to the use of transcranial brain stimulation. Previous studies in the [name] lab that used comparable devices (i.e., the commercial, CE-certified Neuroconn Plus stimulator) have always been classified as “non-significant risk” by the full UNC IRB. The Neuroconn Plus stimulator and the XCSITE100 stimulator are electrically equivalent and provide the same stimulation.

The XCSITE100 is the first non-invasive brain stimulator designed for research purposes to provide an active sham for tACS and record the stimulation output for later validation. This stimulator may apply either tDCS or tACS for up to 40 minutes (2400 seconds) with appropriate current ramp-up at the beginning of stimulation and ramp-down at the end of stimulation. Both tDCS and tACS may be applied for currents between 100 μ A and 2 mA (peak-to-peak for tACS).

The stimulator has two main components:

1. Android tablet with user interface application (i.e., App)
2. Stimulator with:
 - a. Microprocessor
 - b. Function generator chip
 - c. Voltage controlled current source
 - d. Safety circuitry

To ensure appropriate blinding for each stimulation session, there are designated unblinded individuals to ensure the appropriate stimulation parameters are applied to each participant. These individuals will not interact with participants and will only be involved with the creation of a study file and validation of stimulation waveform.

SAFETY FEATURES

Current Sensor Circuit. A 33.2 Ω sense resistor is placed in series with the stimulation electrodes on the high side. Since high-side current sensing is used, any short circuit of the electrode terminals to ground will be detected. The stimulation current flows through this resistor and creates a voltage. The voltage across this resistor is sensed and amplified by the AD628 difference amplifier. The gain of the difference amplifier is set to 9.9039. The current sensor voltage is then shifted before it is read by the microprocessor and the hardware current safety feature.

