11 RECRUITMENT STRATEGY

Potential subjects will have already identified themselves by participating in our diagnostic study. Subjects who will enter the experiment will be those women who demonstrate the presence of PMDD, defined by the demonstration with daily mood ratings of a 30% or more increase in mean affective symptom ratings in the seven days prior to menses (luteal phase) compared with ratings during the seven days following the cessation of menses (follicular phase).

Based on when potential subjects are first identified as meeting criteria, they will either be recruited (and screened) at the second visit of the diagnostic feeder study, or they will be contacted by phone and re-screened via telephone interview. Given that the exclusion criteria for both the feeder study and this study are similar, the re-screening process is simply used to confirm that nothing has changed since they participated in the feeder study.

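### The family-history exclusion that the protocol cites as a seizure safeguard is missing from both exclusion lists; secondarily, the 2 mA current behind the quoted density has no consistent convention

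*Combined protocol and SAP*

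**What the plan says.** **Family history.** The Risk/Benefit Assessment in section 1.1 says that, to lower a very small theoretical chance of seizure, "we screen and exclude patients with personal and family history of neurological conditions from the study". The Data and Safety Monitoring Plan that follows the synopsis repeats the sentence.

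The synopsis lists "Neurologic disease (e.g. epilepsy or brain tumor") among its exclusions, and section 3.4 lists "Neurologic disease (e.g., epilepsy or a brain tumor"). The only other exclusions in either list that bear on neurological history are traumatic brain injury and brain surgery or implants. Neither list mentions relatives. Section 11 describes re-screening as a check that nothing has changed since the diagnostic study, and gives as its reason: "Given that the exclusion criteria for both the feeder study and this study are similar". The diagnostic study's criteria are not reproduced.

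**Current.** Section 1.1 says "Our stimulation area is 25 cm²" and then "we will use this device at 2mA, resulting in a current density of" 0.08 mA/cm². Sections 4.1 and 4.2 specify 5 × 5 cm pads at F3 and F4 with a return over Cz, and state: "The tACS stimulation will deliver a maximum amplitude of 2mA for a total of 40 minutes of stimulation per session". The device description in section 1, repeated in section 7, gives the top of the output range as "2 mA (peak-to-peak for tACS").

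**The concern.** A protection described in the risk text works only if it is also in the criteria used to enrol. A reader of section 1.1 or the monitoring plan would believe that women with affected relatives are kept out. Someone applying section 3.4 as written has no instruction to ask about relatives. Both accounts cannot describe the same screening.

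The current raises a different question. Section 1.1 rests its minimal-risk statement on low current density, so the current in that calculation should be the one the device delivers. The protocol uses the same number, 2 mA, once as an amplitude and once as a peak-to-peak limit, and does not say whether it applies to each pad or to both together. This also affects the science. Section 6 presents the study as a pilot for a larger trial, and a stimulation setting that can be read in several ways cannot be reproduced with confidence.

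**Working it through.** **Part (a): comparison of the texts.** No arithmetic applies.

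| Place | Woman's own neurological history | Family history |
|---|---|---|
| Section 1.1, Risk/Benefit Assessment | Excluded | Excluded |
| Data and Safety Monitoring Plan after the synopsis | Excluded | Excluded |
| Synopsis, exclusion criteria | Neurologic disease, brain injury, surgery or implants | No item |
| Section 3.4, exclusion criteria | Neurologic disease, brain injury, surgery or implants | No item |
| Section 11, diagnostic-study criteria | Called similar, not listed | Cannot be determined |

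The two narrative texts agree with each other, and the two operative lists agree with each other. The lists differ from the narrative on family history only.

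**Part (b): current and density.** Inputs: 2 mA (sections 1.1, 4.1, 4.2); pad 5 × 5 cm (4.1, 4.2); two frontal pads (4.1, 4.2); tACS limit 2 mA peak-to-peak (sections 1 and 7).

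1. *The protocol's own figure.* Density = current / area. Area = 5 × 5 = 25 cm². 2 / 25 = 0.08 mA/cm². This reproduces section 1.1 and agrees with the nominal settings in 4.1 and 4.2.
2. *2 mA as zero-to-peak, per pad.* Peak-to-peak = 2 × 2 = 4 mA. Against the stated limit, 4 / 2 = 2, so twice the range. Density at the frontal pad is 0.08 mA/cm².
3. *2 mA as peak-to-peak, per pad.* Peak = 2 / 2 = 1 mA. Density = 1 / 25 = 0.04 mA/cm².
4. *2 mA as peak-to-peak, total, split equally over two pads.* Peak per pad = 1 / 2 = 0.5 mA. Density = 0.5 / 25 = 0.02 mA/cm².

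| Reading of 2 mA | Peak density at a frontal pad (mA/cm²) | Against 2 mA peak-to-peak limit |
|---|---|---|
| Zero-to-peak, per pad | 0.08 | 4 mA, outside |
| Peak-to-peak, per pad | 0.04 | 2 mA, at the limit |
| Peak-to-peak, total, equal split | 0.02 | 2 mA, at the limit |

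So 0.08 as a peak density at a frontal pad requires a current outside the stated range. The readings that respect the range give half or a quarter of it.

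**The case against.** **On family history.** The seizure safeguard is largely present: personal neurologic disease including epilepsy, traumatic brain injury, and brain surgery or implants are all excluded. A seizure leads to withdrawal (section 4.7), and a neurology contact is available (section 9). Family history is offered only as a further reduction of a risk already described as very small. Every participant comes through the diagnostic study, whose criteria or screening form may contain the item. All of this stands, and it rules out the inference that the seizure safeguard as a whole is not applied. It does not close the gap, because this protocol asserts a rule that its own lists omit, and an unlisted rule elsewhere cannot be relied on.

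**On current.** The fair reply is that 0.08 mA/cm² is right for 2 mA over 25 cm² and matches the nominal settings. That stands too. The figure is not miscalculated; what is unsettled is the meaning of 2 mA.

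**Stronger readings that do not hold.** A reader might infer that density at the Cz return reaches 0.16 mA/cm² (4 / 25), above the highest prior-study value cited, 0.125. That needs four things at once: a zero-to-peak reading that exceeds the device range, 2 mA at each pad, in-phase currents, and a 25 cm² return. The protocol states none of the four. Keeping to 1 mA peak per pad, with the other assumptions unchanged, gives (1 + 1) / 25 = 0.08.

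A reader might also set 4 mA against the ±3 mA peak software cutoff in section 7. If the sensor sees the summed current, stimulation would stop, so 4 mA would not be delivered. If sensing is per channel, a summed current is the wrong comparison. Either way, the cutoff does not settle which convention the 2 mA follows.

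**Conclusion.** The main point holds on the text alone. A family-history exclusion is asserted in two places as a protection against seizure and is absent from both exclusion lists. How many women this affects cannot be estimated from the documents. The finding is confined to the family-history component, and assumes only that staff work from the listed criteria.

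The secondary point is a conflict of convention. Either 2 mA is zero-to-peak and the output is 4 mA peak-to-peak, twice the stated limit, or it is peak-to-peak and the frontal peak density is 0.04 mA/cm² (0.02 if it is a total shared equally), not 0.08. Every frontal-pad value is at or below the stated figure, so this does not show that risk is understated. Density at the return is not given and cannot be calculated without assuming its area and how the currents combine.

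Neither point is shown to bias an endpoint. The first must be corrected because the protocol contradicts itself on who may enter. The second is a clarification that belongs in the same amendment.

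**What to change.** 1. Reconcile section 1.1 and the Data and Safety Monitoring Plan after the synopsis with the synopsis exclusions and section 3.4, so that the rule on family history reads the same in all four places. Which rule applies is for the clinical team.
2. Reconcile the current in sections 1.1, 4.1 and 4.2 with the device description in sections 1 and 7. State it once, as peak or peak-to-peak and as per pad or total. Give the return-electrode area, and restate density on that basis at the frontal pads and at the return. Which current applies is for the clinical and device team.

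The cost is amendment wording and one short recalculation, plus possibly one line on the screening checklist, depending on which rule is confirmed. The sample size and statistical analysis do not change.

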Previous studies employing tACS, a non-invasive, non-pharmacologic procedure, have shown tACS to be safe and devoid of serious adverse effects. However, tACS does have some mild side effects, such as transient mild tingling, burning, or itching under the electrode sites. In our experience to date, subjects have reported either absent or mild side effects, and there was no difference between the groups with the exception of “flickering lights” (or phosphenes, $p = 0.014$) (Alexander et al., in preparation). Nonetheless, we will employ the following safety measures: subjects will be told that they can stop the stimulation at any time during the procedure and research personnel present during these sessions will also check in with the subject periodically during the stimulation to see whether they are comfortable.. Each subject will receive a semi-structured interview at the conclusion of the stimulation, and any side effects of greater than mild severity will be reported to the study PI. Possible side effects will be more formally evaluated with the daily rating forms, which will ask the subject to rate physical symptoms such as fatigue, headache, pain as well as any symptoms (which the subject can provide in text in the DRSP). The study coordinator will review the subjects’ daily rating forms daily. The PI will review adverse events and side effects in an aggregate format across all subjects enrolled on a quarterly basis. Substantial clinical worsening (compared with the baseline cycles) may result in a subject’s discontinuation from the study, at the discretion of the PI. Development of suicidal ideation more than just passive ideation (i.e., sometimes I feel like life is not worth living – not uncommon in women with PMDD in their symptomatic phase) for any reason or any unanticipated serious side effect will result in the subject’s discontinuation. Failure of the subject to experience symptom attenuation following the cessation of menses will result in the subject’s evaluation, discontinuation from the study, and recommendation of therapeutic intervention if required. The PI is responsible for the assessment and, where appropriate, the reporting of any adverse effects, and the PI can be reached 24/7. Finally, there is a theoretical likelihood that stimulation of neuronal circuits can lead to seizure. However, no studies have reported seizure as a side effect in recent trials of transcranial stimulation for depression or schizophrenia. To further minimize this very small, theoretical likelihood of a seizure, we screen and exclude patients with personal and family history of neurological conditions from the study.

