4.4 Unscheduled visits: not applicable

4.5 Concomitant Medication documentation: not applicable

4.6 Rescue medication administration (if applicable)

4.7 Subject Completion/ Withdrawal procedures: While extremely unlikely, any subject who becomes pregnant or who experiences a seizure during this study will be withdrawn. Any subject who experiences an acute worsening of mood or appearance of suicidal ideation will be assessed by the PI and may be withdrawn from the study. Subjects will be compensated monetarily for time and effort. For mileage subjects will be reimbursed 34 cents/mile. Compensation structure is as follows:

Participants will be paid \$40 per each tACS stimulation study visit, and an additional \$25 upon completion of the Daily Rating Forms. Total: \$105 per subject

Subjects will be paid at the end of their participation. If a subject is withdrawn by the investigators or withdraws herself, she will be compensated for participation up to the point of withdrawal.

- 4.8 Screen failure procedures:** As potential subjects will have been identified as appropriate through the related diagnostic screening protocol, we do not anticipate screening failures. In the case that a subject enrolls to participate in the trial but does not meet criteria, the study coordinator completing the screening process will clearly explain why the subject does not meet criteria. However, in the case that a subject does not qualify based on acute suicide risk, [name] will evaluate the subject and determine the appropriate clinical intervention.

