5 STUDY EVALUATIONS AND MEASUREMENTS

- **List variables that will be abstracted from medical charts** – not applicable
- **Describe baseline evaluation** –
 - 1) Prior to enrollment in the tACS study, subjects must meet diagnostic criteria for PMDD. The DRSP (Daily Record of Severity of Problems), a validated daily symptom chart widely used for the diagnosis of PMDD, includes 21 items grouped into 11 domains that address the criterion of symptoms in PMDD (depression, anxiety, lability, anger, interest in activities, concentration, lethargy, appetite, sleep, control, and physical symptom). Each item is rated on a scale of 1 (“note at all”) to 6 (“extreme”). Using the DRSP, subjects must show symptom severity of 4 or greater for two days on a core emotional symptom in the luteal phase, absence of symptom severity during the follicular phase, and a 30% or greater increase in severity of symptoms in the 7 days preceding menses with 7 days following the end of menses.
 - 2) left prefrontal alpha power prior to tACS, obtained with EEG

Describe how measurements will be taken.

 - 1) symptom measures are self-reported on DRSP via Qualtrics survey tool; 2) EEG will be obtained for 8 minutes, with two-minute alternating intervals of eyes open and eyes closed.
- **Describe rating scales, tests, psychological tools, laboratory evaluations, etc.**
 - 1) Resting state EEG (RSEEG) recordings will be completed at several times during the course of the study. Subjects will complete an alternating eyes open/eyes closed RSEEG immediately before and after the 40 minutes of stimulation. This measure is used to determine the immediate after-effects of tACS on brain activity, specifically on alpha oscillation power, as well as how consecutive stimulation sessions may affect these after-effects.
 - 2) DRSP - Daily Record of Severity of Problems (DRSP) ratings daily throughout the study administered electronically via Qualtrics survey platform. This 20-item self-report rating scale assesses physical and mood symptoms that accompany ovarian hormone changes and is often used as a dimensional measure of PMDD.

5.1 Efficacy Evaluation (if applicable): Comparison of left prefrontal alpha power in post-tACS EEG compared with that preceding the procedure; comparison of degree of change in prefrontal alpha in follicular vs luteal phase.

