6.3 Statistical Methods

Baseline Data: alpha oscillations in left frontal cortex before stimulation; severity of luteal phase symptoms in screening DRSP.

Efficacy Analysis: This is repeated, single intervention (tACS) administered during the follicular and luteal phase. Change in left prefrontal alpha power on EEG is the primary outcome. Effect of menstrual cycle phase is the secondary outcome. We will use a t-test of pre-post changes to examine effects of tACS on left prefrontal alpha oscillations (primary outcome) and differences in effects as function of menstrual cycle phase (secondary outcome). There will be two levels of each of the two repeated within-subjects measures (pre vs post stimulation and follicular vs luteal phase). Order of administration will be assessed by considering order as a between- subjects variable.

Exploratory analysis: Assessment of possible changes in mood will be assessed with linear mixed model regression analysis comparing mean luteal phase core affective symptoms (depression, irritability) after stimulation with means during baseline.

Pharmacokinetic Analysis (if applicable): not applicable

Safety Analysis - The PI will review any adverse effects and will quarterly review aggregated data, which will be recorded descriptively. Safety/ Tolerability will be assessed in two ways: 1) with somatic symptoms contained within the DRSP, completed daily, and with symptoms reviewed daily by the research coordinator. Any symptoms of moderate or greater severity appearing proximate to the tACS session will be reported to the PI. 2) with a semi-structured interview at the end of each tACS session, inquiring about possible side effects during the procedure (e.g., tingling, flickering lights, itching, burning sensation, headache, neck pain, scalp pain). Side effects of moderate or greater severity will be reported to the PI, who will also review aggregate data at the end of the experiment.

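### The side-effect interview, a primary safety measure, does not name sleepiness and has no pre-stimulation reference, and the plan's two accounts of the team's experience with sleepiness need reconciling

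*Combined protocol and SAP*

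**What the plan says.** **Team experience, first account.** Section 1.1 (Risk/Benefit Assessment) states: "In our experience, increased sleepiness and flickering lights were more common than sham stimulation". It gives no counts, rates or test.

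**Team experience, second account.** The data and safety monitoring plan in the synopsis states that "subjects have reported either absent or mild side effects, and there was no difference between the groups with the exception of" one symptom. That symptom is flickering lights, with a p-value of 0.014. It cites one manuscript in preparation. The sentence does not say what the groups were.

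**Interview.** The synopsis (Safety Evaluations) lists the semi-structured interview and the DRSP physical items as the primary safety measurements. Section 6.3 (Safety Analysis) places the interview at the end of each session, "inquiring about possible side effects during the procedure (e.g., tingling, flickering lights, itching, burning sensation, headache, neck pain, scalp pain"). Effects of moderate or greater severity go to the principal investigator.

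**Other channels.** The synopsis says that on the daily form women will "rate physical symptoms such as fatigue, headache, pain as well as any symptoms (which the subject can provide in text in the DRSP"). Section 5 lists the DRSP domains as "depression, anxiety, lability, anger, interest in activities, concentration, lethargy, appetite, sleep, control, and physical symptom". Section 9, part II, has the coordinator and the tACS technician watch for side effects during and after stimulation.

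**The concern.** Sleepiness is one of only two effects that section 1.1 reports as more frequent than with sham, but the interview does not name it. Whether it is recorded then depends on the interviewer or on the woman raising it, and that may differ between sessions.

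The interview is also held only after stimulation. Sections 3.1 and 3.2 describe an open-label study without treatment groups, and each woman is stimulated once in the follicular phase and once in the luteal phase. Symptoms are expected to differ between those phases. Headache, pain or tiredness already present on arrival can be recorded afterwards as a side effect, and more readily in the luteal session. The tolerability summary would then mix the disorder with the procedure, in a pilot meant to inform a larger trial.

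**Working it through.** No arithmetic decides this point. The only figure attached to the two accounts, p = 0.014 for flickering lights, cannot be reproduced because the documents give no counts, group sizes, test or sidedness. The check sets the texts side by side.

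**1. The two accounts.**

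| | Section 1.1 | Synopsis, monitoring plan |
|---|---|---|
| Effects in excess | sleepiness, flickering lights | flickering lights only |
| Comparator named | sham | not named |
| Evidence | none stated | one p-value, one unpublished manuscript |

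If both describe the same comparison and the same standard of difference, they disagree on sleepiness. The documents do not establish either condition. Section 1.1 also shows that the team's experience spans studies in schizophrenia and in depression.

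**2. The interview list.** Section 6.3 names seven examples. Four of them (tingling, itching, burning, headache) are effects for which section 1.1 cites a review finding no significant difference from sham. Flickering lights is listed. Sleepiness is not.

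**3. What the other channels add.**
- *DRSP content.* Fatigue, lethargy, sleep and free text all offer a route, so the gap is partial.
- *DRSP timing.* Section 6 describes the ratings as made at night. A structured nightly score does not by itself locate sleepiness at the session, although a free-text entry could.
- *DRSP specificity.* Section 5 presents lethargy and sleep as domains of the disorder itself. A raised luteal score does not separate session from illness.
- *DRSP start.* Sections 4 and 5 call the ratings daily throughout the study, but the synopsis and sections 4.1 and 4.2 start them after the first session. On that timing there is no same-cycle rating before session one. The feeder-study ratings come from other cycles.
- *Staff monitoring.* Section 9 provides for it without naming items. Section 1.1 says the staff member asks about comfort.

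**4. Reach.** 20 women × 2 sessions = 40. Section 3.3 plans 22 enrolled, counted from the first session. With no drop-out that is 22 × 2 = 44. With two drop-outs after session one it is 22 + 20 = 42. These are counts of sessions at which the interview is used, not estimates of missed events.

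**5. What a reference before stimulation adds.** An item recorded only afterwards may be (a) present on arrival and unchanged, (b) present and worse, or (c) new. The planned interview does not systematically separate these. The same list asked before and after does.

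**The case against.** The strongest reply is that the plan already covers this. The interview list is introduced as examples and the interview is semi-structured, so leaving an item out does not exclude it. Staff monitor side effects during and after stimulation. The DRSP covers fatigue, lethargy and sleep, accepts free text and is reviewed daily, and section 6.3 already sends moderate or worse symptoms arising near a session to the principal investigator. This stands: a reader might infer that sleepiness will go uncounted, and the documents do not support that.

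It is also said that the two accounts can both be true, for instance if they come from different studies, or if sleepiness was more frequent without reaching significance. That stands too. A reader might infer a flat contradiction, or that the synopsis denies a difference from sham. It names no sham group.

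A reader might further connect the mileage payment ("For mileage subjects will be reimbursed 34 cents/mile") with women driving home sleepy. A reimbursement rate shows neither who drives nor who leaves sleepy, so nothing here rests on it.

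Finally, without a sham arm a before-and-after list cannot attribute sleepiness to the current, because sitting through a 40-minute session may cause it. That is correct and limits the gain. It does not remove the narrower benefit of separating what was present on arrival from what appeared or worsened. Counting only new or worse items would narrow the safety table, so all reported items should be shown as well.

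**Conclusion.** The point holds as a minor improvement in safety ascertainment. The two accounts of the team's experience are unreconciled. A primary safety measure does not ask about sleepiness consistently and has no reference before stimulation. The remaining channels capture sleepiness in part but do not tie it reliably to a session.

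The conclusion assumes that the interview will be run from the examples in section 6.3 and that DRSP ratings start after the first session, as the synopsis and sections 4.1 and 4.2 say. If an interview form already lists sleepiness, that part falls away and the lack of a pre-stimulation reference remains.

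The interview applies at 40 to 44 sessions. The documents give no sleepiness rate, so no number of missed or misattributed events can be derived. No endpoint, sample size or efficacy analysis is affected.

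**What to change.** 1. Reconcile section 1.1 with the monitoring plan in the synopsis from the team's source data: state which study or studies each sentence describes, the comparator, and the counts for sleepiness and flickering lights.
2. In section 6.3, turn the examples into a fixed short list that includes sleepiness, graded on the mild, moderate and severe scale already defined in section 9. Keep an open question for anything else.
3. Ask the same list immediately before stimulation at both sessions.
4. Tabulate by phase the items that are new or worse after stimulation, alongside all items reported. Leave the existing reporting to the principal investigator unchanged.

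The cost is one added item, some wording, and an estimated two minutes per session: 2 × 40 = 80 to 2 × 44 = 88 minutes over the whole study. Stimulation and two EEG recordings take 40 + 2 × 8 = 56 of the up to 90 minutes allowed, leaving 34 for electrode placement and questions. The table will still not separate the effect of the current from that of sitting through the session, and the report should say so.
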